The skeletal muscle of aging adults differs from young adults with lower 5' adenosine monophosphate-activated protein kinase (AMPK) activity, a selective decrease in type II muscle fibers, accumulation of intramyocellular lipid, lower capillary-to-muscle fiber ratio, and fewer mitochondria.²⁶⁻³⁰ Both metformin and exercise can stimulate the phosphorylation of AMPK, an enzyme that can regulate the transcription of genes responsible for switching muscle fiber types from glycolytic to more oxidative, fatigue-resistant fibers, lowering muscle lipid accumulation, stimulating angiogenesis and increasing mitochondrial biogenesis (Fig 1).³¹⁻³⁴

Aerobic exercise can maintain or improve muscle mass and function in older adults.³⁵ Histologic changes in muscle accompanying exercise training in older adults include decreased diacylglycerol and ceramide content, increased capillary density, increased mitochondrial content and activity and a switch from type IIB to more oxidative IIA fibers.³⁶⁻³⁸ Similar studies to evaluate the effects of metformin on muscle mass, function and histology have not yet been performed in older adults.

However, animal studies suggest that pharmacologic activation of AMPK results in histologic changes in muscle similar to exercise. Treatment of animals with metformin or another AMPK agonist, 5-

aminoimidazole-4-carboxamide ribofuranoside (AICAR), increased fatty acid oxidation and decreased diacylglycerol and ceramide content in skeletal muscle.³⁹⁻⁴³ Increased expression of vascular endothelial growth factor and skeletal muscle angiogenesis also occur in mice treated with AICAR.^{44, 45} Increased activity of mitochondrial enzymes and expression of mitochondrial protein in muscle with AICAR and increased mitochondrial density with another AMPK activator, β -guanadinopropionic acid, may be mediated through downstream activation of peroxisome proliferator-activated receptor-gamma coactivator-1alpha (PGC1- α).^{34, 46-49} AICAR-treated rats appeared to have a switch from type IIB fibers to more oxidative type IIX fibers similar to endurance trained rats.⁵⁰ While AICAR and metformin in animals can lead to the histologic changes in muscle in our proposed mechanistic framework (Fig. 1), the effect of metformin on human muscle composition remains to be confirmed.

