The secondary hypothesis is that the muscle composition of metformin-treated participants will have a greater increase in number of oxidative fibers, decrease in intramyocellular lipid, increase in capillary density and increase in the number of mitochondria than placebo-treated participants. These outcomes have been chosen based on our hypothetical framework in Figure 1 that was developed from known alterations in these measures in animal models treated with metformin or other AMPK agonists. Quantification of intramyocellular lipid, fiber types, capillary density and mitochondrial content will be obtained through histochemical analyses of muscle biopsy specimens as described in the Muscle Biopsy section.

Study Visits

All visits will be completed at VAPORHCS and/or at OHSU.

Screening Visit

IRB-approved study personnel will have a full discussion with the potential subject, including information on study visits, procedures, risks, and benefits. All participants will be informed of their right to withdraw from the study at any time. The principal investigator will answer any questions from participants at any time. Participants will provide written informed consent prior to any study procedures being performed. A copy of the IRB-approved informed consent and signed HIPAA authorization form will be given to the subject. Demographic information (including age, gender, and race) and lifestyle factors (including physical activity, smoking history and alcohol intake) will be obtained. Medical history (including self-reported physician medical diagnoses), drug allergies/adverse effects and medications will be obtained. Height, weight and blood pressure (BP) will be measured. Criteria for exclusion criteria will be formally reviewed. Participants must demonstrate that they are able to ambulate 400 meters without assistance. Laboratory assessment for B12 levels and liver, kidney and clotting function will be performed. The total amount of blood drawn will be 10 ml. Labs will be drawn for fasting glucose to identify participants with IFG. All labs will be ordered after consent is obtained. Participants will be instructed to remain fasting for 12 hours prior to the study day. This visit could take up to 2 hours. Participants who have IFG will be scheduled to attend a Baseline visit if the Screening visit does not reveal presence of an exclusion criterion.

Baseline Visit

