The payments are reasonable and commensurate with the expected contributions of the subject. Each annual study visit is 2-3 hours. Baseline and annual visits include a fasting blood draw, height, weight, blood pressure, questionnaires, performance tests, and DXA. The procedures at every 6 month study visits (in between annual visits) are only fasting labs and questionnaires for all participants. For the muscle biopsy substudy, there will be a separate 1-2 hour visit at baseline and an additional 1 hour added to the 6 month visit.

Payments are fair and appropriate and do not constitute (or appear to constitute) undue pressure or influence on, or coercion of, the prospective research subjects to volunteer for or continue participation in the research study.

Statistical considerations

Sample Size and Power

Based on prior observational findings, there was a significant difference (2.2%, p< 0.01) in the percentage change in appendicular lean mass over 3.5 years between metformin-treated and untreated men. The sample size required for 80% Power to detect this difference and reject the null with SD=4% and α =0.05 for an unpaired, 2-sided t-test is 106 study participants (53 in each group). We plan to enroll 300 participants and, of those, randomize 120 (60 in each group) to allow for potential drop outs due to noncompliance and other reasons (7.5-10%). While 8-11% of participants may

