progress to diabetes yearly,^{72, 79, 80} all efforts will be made to retain these participants in the study and to include them in intent-to-treat analyses. The Power and effect size estimates for gait speed (SD=0.19) for α =0.05 for 60 participants and 53 participants per group are illustrated in the graph (Fig. 8) and based on our preliminary data in older women. The sample size of 60 participants per group will have 73% Power to detect a 0.09 m/s difference in gait speed. Within each group, 16 participants will be randomly selected and consented to undergo muscle biopsies at baseline and 6 months for secondary analyses of muscle histologic changes with metformin vs. placebo treatment. There is an expected change in these histologic measures within 6 months given prior studies that detect changes in AMPK activation, ATP concentration and insulin sensitivity prior to 6 months with use of metformin.^{3, 4} Estimated effect sizes of the difference in histologic measures between the two groups after 6 months are shown below in Table 3. While this study is adequately powered for 3 year outcomes in muscle loss, interim analyses may be performed by a Data Monitoring Committee (managed by the VA CSRD), given blinding of the primary investigator to the intervention, and the trial may be terminated early if a significant difference in the primary outcome between metformin- and placebo-treated groups is noted before 3 years.

	SD	70%	80%	90%
Capillary Density (AU)	0.35	0.32	0.36	0.42
IMCL (AU)	0.50	0.46	0.51	0.59
SDH (AU)	0.50	0.46	0.51	0.59
% Type I Fibers	24.0	21.8	24.6	28.4

Table 3 Estimated detectable difference in muscle histology measures at 80 and 90% Power

SD derived from measures in older insulin-resistant adults³⁶

Statistical Analyses

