To assess a difference in the primary outcomes of change in muscle mass and performance between metforminand placebo-treated groups, longitudinal (mixed effects) models will be used to estimate the trajectory of change. These models will account for correlation of outcomes within subjects and allows for those with missing followup data to be included in analyses. Four measures of muscle mass and performance (baseline, year 1, 2 and 3) are the outcomes in separate models. These will be modeled as a linear change over time, and other functional changes (squared, cubic and quadratic) will be evaluated. In the best fitting model, an interaction between time and group (metformin vs. placebo) will be included in the model to determine if changes in muscle mass/performance differ between the two groups. For the secondary outcomes of muscle histology, the discrete change in measures of mitochondrial content, muscle capillary density, percentage of fiber types and intramyocellular lipid content over 6 months will be calculated. The absolute and percentage changes in these measures will serve as the outcome in linear regression models with treatment group as the dichotomous exposure. Nonlinear associations between the exposure and outcomes will be evaluated with higher order terms. For the analyses of primary and secondary outcomes, potential confounders including demographic information, physical activity, diet, lifestyle factors, medical history and medication use are expected to be evenly distributed between the groups in a random fashion; nevertheless, we will evaluate for potential confounding by these factors and include them in multivariable models if they are significantly associated with our exposure and outcome and modify the effect size by >10%. There is no anticipated gender difference in the study outcomes, so the study has not been powered to detect a significant interaction by gender. However, the primary and secondary outcomes will also be stratified by gender to explore if there is a gender-specific muscle response to metformin. To account for missing data, multiple imputation modeling will constructed from participants with complete data. Participants with missing data will have those values imputed at each time point multiple imputation.⁸² Results will be reported with and without imputed values.

Data Integrity

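### Each histology measure has two co-equal outcomes, absolute and percentage change, with no lead scale, and the only powered fiber measure, % Type I, does not cover the within-type-II shift cited in the rationale

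*Combined protocol and SAP*

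**What the plan says.** **Outcome scale.** For capillary density, mitochondrial content, fiber-type percentages and intramyocellular lipid, Statistical Analyses takes the change over 6 months and continues: "The absolute and percentage changes in these measures will serve as the outcome in linear regression models with treatment group as the dichotomous exposure". It gives no lead scale, no rule for disagreement and no multiplicity rule for histology. The next sentence adds: "Nonlinear associations between the exposure and outcomes will be evaluated with higher order terms".

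**Size and power.** Under Sample Size and Power, "Within each group, 16 participants will be randomly selected and consented to undergo muscle biopsies at baseline and 6 months". Table 3 lists detectable between-group differences in arbitrary units or fiber percentage points for capillary density, IMCL, SDH and % Type I fibers. Its footnote reads "SD derived from measures in older insulin-resistant adults". It does not say that these are SDs of a change, and it gives no SD for a percentage change.

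**Fibers.** Secondary outcome measures hypothesises a "greater increase in number of oxidative fibers" without saying which types count. The Study Procedures section counts types I, IIa and IIx. The mechanism section cites, for exercise training in older adults, "a switch from type IIB to more oxidative IIA fibers". For the AMPK agonist AICAR in rats it cites a IIB to IIX switch. It also speaks generally of switching from glycolytic to more oxidative fibers.

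**The concern.** With two co-equal outcomes per measure, the plan does not say which result answers the hypothesis when one scale reaches p<0.05 and the other does not. Only one of the two has a power basis. For fiber type, the second outcome is a percentage change in a percentage.

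The fiber hypothesis has a further gap. If metformin moves fibers within type II, % Type I need not change, so the only fiber measure with a power figure could be flat while the cited shift takes place. A reader of Table 3 would not see this.

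At stake is the clarity of the trial's only histologic test of mechanism, for which 32 people are asked for two biopsies each. The primary comparison of lean mass and performance is not affected.

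**Working it through.** **1. Reproduce Table 3.** Inputs: 16 per arm and the SDs from Table 3. Two-sided α = 0.05 with a t-test is stated for the primary outcome and assumed here for histology. The detectable difference is d × SD, where d solves

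power = P(|T| > t₀.₉₇₅,₃₀), with T noncentral t, 30 df, noncentrality d√(16/2).

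This gives d = 0.908, 1.024 and 1.185 at 70, 80 and 90% power.

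| Measure | SD | Computed 70 / 80 / 90% | Stated |
|---|---|---|---|
| Capillary density | 0.35 | 0.318 / 0.358 / 0.415 | 0.32 / 0.36 / 0.42 |
| IMCL, SDH | 0.50 | 0.454 / 0.512 / 0.592 | 0.46 / 0.51 / 0.59 |
| % Type I | 24.0 | 21.78 / 24.57 / 28.43 | 21.8 / 24.6 / 28.4 |

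The arithmetic of Table 3 holds to within rounding. It covers raw units only.

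**2. Do the two scales agree?** Simulation, 20,000 substudies per setting, 16 per arm, t-tests on (6-month − baseline) and on (6-month − baseline)/baseline. Assumptions not in the documents: lognormal measures, CV 0.3 to 0.7, correlation ρ 0.3 to 0.7.

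- No effect: at least one scale has p<0.05 in about 6 to 7% of substudies per measure, against 5% for one scale.
- Effect of 1.024 SD: the scales disagree on p<0.05 in about 4 to 21% per measure. Modelling the effect as additive or as proportional moves the ends by about a point.
- Both scales significant in opposite directions: 0.0% in every setting run.

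Across four measures taken as independent, the chance of at least one false positive is:

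- one scale: 1 − 0.95⁴ = 18.5%
- either scale: 1 − 0.94⁴ = 21.9% to 1 − 0.93⁴ = 25.2%

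The second scale therefore adds about 3 to 7 points. The larger part, 18.5%, comes from four unadjusted tests.

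**3. Which absolute-scale analysis?** If Table 3's SD is that of a single time point and is equal at both visits, the SD of a change is SD × √(2(1 − ρ)), and the residual SD after linear baseline adjustment is SD × √(1 − ρ²).

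| ρ | Change | Baseline-adjusted |
|---|---|---|
| 0.3 | 1.18 SD | 0.95 SD |
| 0.5 | 1.00 SD | 0.87 SD |
| 0.7 | 0.77 SD | 0.71 SD |

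So Table 3's 80% holds for absolute change only near ρ = 0.5. In the simulation, power for absolute change at the 1.024 SD effect was about 66% at ρ = 0.3 and 95% at ρ = 0.7. Baseline adjustment is at least as precise at each ρ.

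**4. Fibers.** Since I + IIa + IIx = 100, the change in I equals −(change in IIa + change in IIx). A pure IIx to IIa move makes the last two cancel, so the change in % Type I is 0. As an illustration, assume mean type I of 45% with SD 24, and IIx as 40% of type II. Mean IIx is then 0.40 × 55 = 22%. Moving 30% of it to IIa shifts 0.30 × 22 = 6.6 points (6.5 in simulation). Simulated rejection rates were 4.7% on % Type I, 56% on % IIa and 75% on % IIx. The first is α; the other two depend on the assumed mix and variability.

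**5. Higher-order terms.** For an exposure x coded 0/1, x² = x. A squared or cubic term is collinear with x and cannot be estimated.

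**The case against.** The strongest reply is that these are secondary, mechanistic outcomes in 32 people, that both scales are stated in advance, and that reporting only the favourable one would itself depart from the plan. That stands, and it limits the consequence. It does not say how a split result is to be read.

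It is also fair that Table 3 is a power table and not the list of tests. Statistical Analyses takes fiber types in the plural, so a within-type-II shift would still be analysed. What is missing is a power figure for it and a named test of the hypothesis. Because the rationale also speaks generally of glycolytic to oxidative switching, % Type I is not excluded as a measure.

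A noisy baseline biopsy is no decisive argument against percentage change alone, since absolute change subtracts the same biopsy. That is a reason to prefer baseline adjustment.

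Three stronger readings are tempting but not supported:

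- *The two scales could give opposite answers.* Disagreement here means significant on one scale and not on the other. IIa rising while IIx falls is one coherent shift.
- *Testing each fiber type is redundant because they sum to 100.* Three percentages with one constraint leave two free dimensions, and step 4 shows the three types responding differently to one shift.
- *Some disagreement will arise in about half of substudies.* That depends on one chosen setting. With four independent measures, the 4 to 21% range gives 1 − 0.96⁴ = 15% to 1 − 0.79⁴ = 61%, and the documents give no CV or correlation to choose within it.

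**Conclusion.** The concern holds at modest size. The text leaves two co-equal scales per histology measure, and only raw units are powered. The 4 to 21% disagreement and the 6 to 7% either-scale error rest on assumed lognormal measures, CVs and correlations. Lognormality suits a bounded fiber percentage poorly, and part of the disagreement range reflects power changing with ρ. That no lead scale is named, and that Table 3 powers raw units only, follows from the text without simulation.

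That % Type I cannot detect a pure within-type-II shift is algebra and needs no assumption about variability. Which types count as oxidative is a scientific choice the documents leave open: the rationale calls IIX more oxidative than IIB, so placing IIx on the non-oxidative side is not settled by the text.

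The higher-order sentence is a slip that changes no result.

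**What to change.** 1. Name one formal test per histology measure, on the absolute scale in Table 3's units: preferably the 6-month value adjusted for baseline, otherwise absolute change. Report percentage change descriptively, without p-values.
2. Before unblinding, have the investigators name the fiber type or sum that tests the oxidative-fiber hypothesis. State beside Table 3 that the % Type I figure does not cover a within-type-II shift. The documents give no SD from which to add a powered row for another fiber measure.
3. Delete the sentence on higher-order terms of the exposure.

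The cost is a few lines of analysis-plan wording, with no new data or procedures. The small downside is that percentage change loses its formal test. The fix removes the second scale's contribution only. Four unadjusted tests would still carry the 18.5% computed above if independent, so the plan should say whether histology p-values are exploratory or adjusted.

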We have chosen to study metformin in this clinical trial due to the observation that metformin use was associated with an attenuated loss of muscle mass and function in our preliminary studies. While both metformin and thiazolidinediones can upregulate AMPK and PGC1a in muscle to increase muscle fatty acid oxidation, angiogenesis, mitochondrial biogenesis and oxidative muscle fibers for healthier-appearing muscle,^{32, 34, 68} metformin has additional benefits on mortality, microvascular and macrovascular outcomes in patients with type 2 diabetes;⁶⁹ whereas, thiazolidinediones have associated risks of adverse cardiovascular outcomes.^{70, 71}

The VA Research Pharmacy will be used to randomize, dispense, and track blinded placebo and metformin tablets in 3-month supplies. A covariate-adaptive randomization scheme will be used to ensure equal age, gender and race distributions. The investigators and study participants will be blinded to the randomization of the study drug assignments. A 90-day supply of study drug will be mailed every 3 months to participants with a pre-paid envelope for returning unused study drugs for pill counts. An additional 4-day buffer may be included to avoid lapses in study drug administration due to unforeseen complications in medication delivery and/or receipt. To minimize self-limiting gastrointestinal side effects, participants randomized to metformin will begin with an oral dose of 850 mg tablets once daily (taken with meals) for 1 month with titration up to 850 mg twice daily for the remainder of the study. We anticipate an effect on muscle using this dosage, since a significant reduction in peripheral insulin resistance occurs even with a metformin daily dosage of 750 mg.⁶¹ Furthermore, this dose was safe and effective in lowering the risk of diabetes for subjects with prediabetes in the Diabetes Prevention Program.⁷⁵ Plans for monitoring and preventing risks associated with metformin are further discussed under Human Subjects.

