Potential benefits to participants include the detection and potentially earlier treatment of diabetes mellitus. Participants in both metformin and placebo groups will benefit from routine lifestyle modification counseling at yearly visits for prevention of diabetes.

Others may benefit from a greater understanding of the effect of metformin on muscle mass and function in insulin-resistant older adults.

VA Data Monitoring Committee (DMC)

A data monitoring committee will be provided by VA CSR&D. With DMC's experience in the conduct and monitoring of clinical trials, it will assist with ensuring the overall safety of study participants, assessing safety and efficacy of the study intervention, monitoring the overall conduct of the clinical trial including recommendations on recruitment and retention of participants and improvement of study drug adherence, and providing recommendations on stopping or continuation of the trial. SAEs and UPRs will be reported to the DMC. For further details, see the "Instructions for the Review of New (uninitiated) Protocols by DMC Members."

Inclusion of Women and Children

Because sarcopenia is a condition of older age, children will not be enrolled in this study. Women will be included in a proportion reflective of their gender distribution at the VAPORHCS.

Criteria for Discontinuation

Subjects will be withdrawn from further study drug administration in the event of any of the following:

• Diagnosis of diabetes

- If hospitalized for any reason and after 48 hours of discharge, there is evidence of renal dysfunction
- If they require contrast medium and after 48 hours of procedure, there is evidence of renal dysfunction
- Developed lactic acidosis
- Developed renal insufficiency at the level indicated by the FDA ($eGFR < 45 \text{ mL/min}/1.73 \text{ m}^2$).
- Development of B12 deficiency
- Excessive alcohol intake
- Subject withdraws consent
- Significant deviation from the protocol or eligibility criteria in the opinion of the investigator
- Any other reason that in the opinion of the investigator, would justify removing the subject from the study

There are no pre-defined stopping rules for termination of the study.

VA Research:

The following are the components of the study which will be conducted at the VAPORHCS:

- Advertising
- Recruitment
- Study visit activities at Screening, Baseline, half-yearly visits, and annual visits
 - Consent
 - Height, weight
 - o Blood pressure
 - Demographics
 - Medical history

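### The covariate entry rule shuts the balancing factors (age, gender, race) out of the primary models, and the histology models omit the baseline biopsy value: power is lost, without bias

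*Combined protocol and SAP*

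**What the plan says.** Under *Study Drug*: "A covariate-adaptive randomization scheme will be used to ensure equal age, gender and race distributions".

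Under *Statistical Analyses*, the primary outcomes go into mixed models: "Four measures of muscle mass and performance (baseline, year 1, 2 and 3) are the outcomes in separate models". The treatment test is the one for which "an interaction between time and group (metformin vs. placebo) will be included in the model". The candidates for adjustment, in primary and secondary analyses alike, are "potential confounders including demographic information, physical activity, diet, lifestyle factors, medical history and medication use". The plan will "include them in multivariable models if they are significantly associated with our exposure and outcome and modify the effect size by >10" percent. No sentence makes age, gender or race a fixed term, alone or with time. The gender-stratified analysis is exploratory and covers neither age nor race.

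For the biopsy substudy: "The absolute and percentage changes in these measures will serve as the outcome in linear regression models with treatment group as the dichotomous exposure". No baseline value is named, although *Sample Size and Power* plans one for everybody: "Within each group, 16 participants will be randomly selected and consented to undergo muscle biopsies at baseline and 6 months".

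**The concern.** The entry rule is a confounder-screening rule from observational work. In a randomized trial a baseline covariate is worth including because it predicts the outcome; its association with treatment is chance. Here the design also removes even that chance association for the three factors it balances, so the rule's first condition excludes exactly the covariates the analysis should carry.

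Balanced allocation makes the treatment estimate less variable than under simple randomization, to the extent that the factors predict the outcome. A model without them still counts their contribution as residual noise. Its standard error is then too large, the test is conservative, and the precision bought by the allocation scheme is not used. The scheme also means that an analysis ignoring the factors does not reflect how treatment was assigned.

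For histology the issue is different. A change score uses the baseline value with a fixed coefficient of 1. Regression on baseline estimates the coefficient and does at least as well, apart from one degree of freedom and a small imbalance penalty. With 32 participants this can matter.

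**Working it through.** **1. The plan's own figures.** Exact two-sided t-tests at alpha 0.05:
- Lean mass: difference 2.2, SD 4, 53 per group gives 80.1% power (plan: 80%).
- Gait speed: difference 0.09, SD 0.19, 60 per group gives 73.0% (plan: 73%).
- Table 3 at 80% power, 16 per group: SD 24 gives 24.6, SD 0.50 gives 0.51, SD 0.35 gives 0.36. All match.

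**2. Can the balancing factors enter?** The documents give neither the algorithm nor the demographic mix (women: "Women will be included in a proportion reflective of their gender distribution at the VAPORHCS"). Assumed: biased-coin minimization (0.8) on age group, sex and race, with 10% women and 15% non-white. A balancing factor was significantly associated with treatment in 0.03–0.05% of tests and entered the model in at most 0.02%. A second simulation (120 participants, 3,000 runs) gave 0%, 0.03% and 0% for age, gender and race, with at most 0.03% of trials passing the full rule.

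**3. Primary test.** Let R² be the share of variance in individual slopes explained by the three factors (assumed split: 80% age, 10% sex, 10% race). With perfect balance the true standard error is √(1−R²) times the one the unadjusted model reports, so type I error tends to 2Φ(−1.96/√(1−R²)):
- R² = 0.05: 1.96/0.975 = 2.01, giving 4.4%
- R² = 0.10: 1.96/0.949 = 2.07, giving 3.9%
- R² = 0.20: 1.96/0.894 = 2.19, giving 2.8%

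Simulation allows for imperfect balance. The effect is 2.2 and the SD 4 over follow-up. Arrows run from unadjusted to pre-specified factor-by-time terms.

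| Setting | R² | SE ratio | Power, % | Type I error, % |
|---|---|---|---|---|
| Mixed model, 4 visits, N = 120, 10% dropout | 0.05 | 0.978 | 83.6 → 85.2 | 4.2 → 4.6 |
| | 0.10 | 0.953 | 83.3 → 86.3 | 4.1 → 4.7 |
| | 0.20 | 0.898 | 85.7 → 90.4 | 3.1 → 4.4 |
| Per-person slopes, N = 106, no dropout | 0 | 1.003 | 80.1 → 79.8 | – |
| | 0.05 | 0.978 | 80.3 → 81.5 | 4.6 → 5.0 |
| | 0.10 | 0.951 | 80.7 → 83.6 | 4.3 → 5.0 |
| | 0.20 | 0.897 | 81.7 → 87.8 | 3.5 → 5.2 |

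The N = 120 rows use 3,000 runs each (Monte Carlo SE about 0.4 points for type I error, 0.6–0.7 for power); the N = 106 rows use 30,000. The plan's rule gave the same rejection rates as no adjustment. The second simulation averaged 2.20 for a true effect of 2.2, with and without adjustment, so there is no bias.

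Main effects alone do not help: the SE of the time-by-group term was 0.252, against 0.251 unadjusted and 0.239 (R² 0.10) or 0.225 (R² 0.20) with time interactions. The subject effects already absorb differences in level. For the same reason baseline lean mass and performance need no extra term, since baseline is one of the four repeated outcomes.

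**4. Histology.** Let r be the correlation between baseline and 6-month values (not in the documents). With cross-sectional SD 24, the change-score variance is 2(1−r)·24² on 30 df. The baseline-adjusted variance is (1−r²)·24² on 29 df, averaged over chance baseline imbalance. The ratio of the two variances is (1+r)/2. Detectable Type I fiber difference at 80% power:

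| r | Change score, SD 24 cross-sectional | Baseline-adjusted | Ratio | Baseline-adjusted if SD 24 is the SD of change (change score: 24.6) |
|---|---|---|---|---|
| 0.3 | 29.1 | 23.9 | 0.82 | 20.2 |
| 0.5 | 24.6 | 21.7 | 0.88 | 21.7 |
| 0.7 | 19.0 | 17.9 | 0.94 | 23.1 |
| 0.9 | 11.0 | 10.9 | 0.99 | 24.4 |

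At r = 0.5, IMCL and SDH go from 0.51 to 0.45 and capillary density from 0.36 to 0.32. The change-score test keeps its level (simulated alpha 0.048–0.052), so this omission costs power only. In a given trial, a chance baseline imbalance moves the change-score estimate by −(1−r) times that imbalance.

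**The case against.** The strongest reply is that no promised power is lost. In every scenario above the unadjusted analysis keeps at least 80% for lean mass, and conservatism is the safe direction. That stands for lean mass: the loss is measured against a better model. It does not cover gait speed, where the plan itself states 73%. Applying SD·√(1−R²) there gives about 77% at R² 0.10 and 82% at R² 0.20.

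The sizes also rest on inputs the documents do not give, and the plan anticipates no gender difference in the outcomes. True. But the preliminary cohort analyses adjusted change for age (walk time in men), demographics (lean mass) and age and race (walk speed in women), so some prognostic value is plausible.

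A technical caution stands as well. The SE ratios are close to √(1−R²), so R² here acts as a share of observed slope variance, measurement error included. If half of that variance were error, factors explaining 10% of true slope variance would cut the SE by only about 2.5% (√0.95 = 0.975), close to the R² = 0.05 row.

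Finally, change from baseline is a valid analysis of a secondary outcome, and at r near 0.9 the gain is negligible. Both are correct.

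**Conclusion.** The concern holds as an efficiency point. The rule in practice excludes age, gender and race. If they predict change, the primary tests are conservative (type I error about 3.1–4.2% with 120 randomized, at R² 0.05–0.20) and give up about 2 to 5 points of power. If they do not, adjusting costs about 0.3 points. For histology, baseline adjustment lowers the detectable difference by 18% at r = 0.3, 12% at 0.5, 6% at 0.7 and 1% at 0.9. R², r, the minimization settings and the demographic mix are assumptions.

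The statement that there is no bias applies to these two omissions. It does not clear the entry rule for covariates measured after randomization: the plan does not restrict activity, diet or medication use to baseline values, which is a separate weakness.

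**What to change.** - Delete the significance and 10% entry rule.
- In the primary mixed models, pre-specify age, gender and race, in the categories the randomization scheme uses, each with its interaction with time. If a nonlinear time form is used, the interactions should follow it.
- For each histology measure, make the regression of the 6-month value on treatment and the baseline value the single test model. Report absolute and percentage change descriptively.
- Do not add further covariates to the histology models by default. Two extra terms that add nothing beyond baseline would raise the detectable Type I fiber difference to 18.6 at r = 0.7 (from 17.9) and 11.3 at r = 0.9, worse than the change score's 11.0.
- Restrict any other covariate to a pre-named list of baseline values.

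This changes wording only; all the variables are already collected. The price is a few degrees of freedom, with little gain if the three factors are weakly prognostic or histology correlates near 0.9 over 6 months. If women are few (about 12 of 120 at the assumed 10%), the gender-by-time term will be imprecisely estimated, but it is there to adjust the treatment comparison and need not be interpreted.
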